### **Risk and Benefit Assessment**

Per the 2006 FDA label for ICG, the only listed risks of ICG administration are urticarial or anaphylactic reactions, which are rare. ICG contains sodium iodide, so caution is recommended in patients with a history of iodide allergy. Per this FDA label, “There are no data available describing the signs, symptoms, or laboratory findings accompanying overdose. The LD 50 after I.V. administration ranges between 60 and 80 mg/kg in mice, 50 and 70 mg/kg in rats and 50 and 80 mg/kg in rabbits.” The FDA arbitrarily suggests a maximum dose of 2mg/kg for human use, and this would be our dosage maximum. The main risk to our study population

would be a small increase in operative time under general anesthesia, which we estimate at an additional 15 minutes. Litvack *et al.* estimated that ICG angiography during their pituitary surgeries required an extra 15-20 minutes of operative time under general anesthesia, which supports our estimation.

The benefits to our study will be visualization of important structures that may be encased by the tumor to avoid injury including the optic nerves, the internal carotids and minor feeding vessels. Also, determination of any residual tumor that may be left during tumor dissection helps prevent or recurrence of the tumor, which will overall decrease the morbidity of these kind of surgeries. We feel that the benefits to the study population markedly outweigh the risks.

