## **Objective**

We intend to demonstrate the feasibility of using a nasal endoscope to perform intraoperative angiography of surgical field, with the goals to evaluate anatomical landmarks and tumor characteristics during skull base surgery and publish a technical note.

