## **Background and Rationale**

The expanded endoscopic endonasal approach (EEA) to the cranial base is increasingly being utilized to address a variety of cranial base pathologies. The more severe complications and morbidities associated with EEA are related to vascular and cranial nerve injury.

The sphenoid sinus is the center and starting point for all the expanded EEA to the ventral skull base. Skull base surgeons rely on anatomical landmarks and neuro-navigation to perform a safe procedure. However, sphenoid sinus pneumatization may vary and anatomical landmarks may not be readily identifiable. In addition, surgeons may not rely exclusively on neuro-navigation since it is not always accurate and precise.

Originally FDA approved for human use in 1959, indocyanine green (ICG) is a tricarboyanine dye with near-infrared fluorescence that has been routinely used in a variety of cerebrovascular procedures since 1972 for real-time noninvasive intraoperative angiography with a multiple-decades-long safety history. It is administered as an intravenous bolus, typically in a dose of 25 milligrams dissolved in 10 milliliters of sterile water. It binds to large plasma proteins within 2 seconds and remains intravascular. ICG is metabolized exclusively by the liver with a plasma half-life of 150 seconds and is excreted

in bile. Angiography is typically most useful approximately 45 seconds after ICG administration in distinct arterial, capillary, and venous phases.

There are only a few reports in the literature describing the use of ICG and the Karl Storz nasal endoscope in EEA for benign ventral skull base lesions. Litvack et al. described the intraoperative use of ICG to successfully differentiate relatively avascular tumor from the capillary-rich normal pituitary gland as well as relatively hypervascular regions of dural invasion without complication. Hide et al. that the real-time observation of the blood supply to the optic nerves and pituitary helps to predict the preservation of their function. Inoue et al. used preoperative 3D-CT and MRI fusion models with intraoperative ICG endoscopy and concluded that the technique allowed distinct visualization of vital structures in cases where tumors had extensively infiltrated the sphenoidal sinus. Additionally, the ICG endoscope was a useful real-time monitoring tool for ETSS.

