## **Proposal**

Based on the positive experience of our Pilot study where ICG accurately demonstrated visualization of perfusion of the pedicled flap posterior nasal arteries and mucosal flap during endoscopic endonasal approaches, we now propose a study in which we will administer ICG during routine EEA for cranial base pathologies in which optic canal decompression, intradural tumor dissection, or dissection of tumor around the internal carotid artery will be necessary.

We anticipate needing no more than thirty-five patients to obtain the necessary information and will either seek further IRB approval or terminate this feasibility study if the necessary information cannot be obtained by the thirty-fifth patient. All surgeries will be performed in a team with [name] (Neurological Surgery) and either [name] (Otolaryngology) or [name] (Otolaryngology). We will use the Storz nasal endoscope, which is already purchased and routinely used at The Ohio State University (OSU), modified as described by Litvack *et al.* to visualize the proposed real-time angiograms. These modifications include a custom xenon light source that produces both the standard white light as well as near-infrared (690-780 nm wavelength) light and a selectable near-infrared filter for the nasal endoscope, both of which will be provided by

Karl Storz free of charge. We intend to administer ICG, which is already widely used during open neurosurgical procedures, to identify anatomical landmarks (such as vascular structures leading to the optic canal and internal carotid arteries) and tumor characteristics (such as tumor vascularization, tissue differentiation, and vessel encasement) during skull base surgery at different stages of endonasal cranial base surgery and tumor dissection: before intradural dissection and during tumor dissection.

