## **Human Subjects**

### 1. Institutional Review Board (IRB) Review and Informed Consent

This protocol and the informed consent document and any subsequent modifications will be reviewed and approved by the IRB or ethics committee responsible for oversight of the study. A signed consent form will be obtained from the subject. The consent form will describe the purpose of the study, the procedures to be followed, and the risks and benefits of participation, and the rights of the participant. A copy of the consent form will be given to the subject and this fact will be documented in the subject's record.

The Principal Investigator or the Study Coordinator will be responsible for submitting any changes to the project to the IRB for approval prior to implementation of the changes. The study will also be submitted for continuing review by the IRB at periods determined by the IRB, at least annually, for the duration of the study.

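### Does the protocol need to list ICG time, injection count and dose as data items because it names added operative time as the main risk?

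*Protocol*

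**What the plan says.** The Objective section defines the aim: "We intend to demonstrate the feasibility of using a nasal endoscope to perform intraoperative angiography of surgical field". It adds that the purpose is to evaluate landmarks and tumor characteristics, and that the product is a technical note.

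The Proposal section states "we now propose a study in which we will administer ICG during routine EEA for cranial base pathologies". It names two stages of use, one before intradural dissection and one during tumor dissection, and caps enrolment: "We anticipate needing no more than thirty-five patients to obtain the necessary information". There is no control group.

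The Risk and Benefit Assessment says the main risk "would be a small increase in operative time under general anesthesia, which we estimate at an additional 15 minutes". As support it cites an earlier pituitary series in which ICG angiography "required an extra 15-20 minutes of operative time under general anesthesia, which supports our estimation". The same section names 2 mg/kg "and this would be our dosage maximum". The Background and Rationale describes the intravenous bolus as "typically in a dose of 25 milligrams dissolved in 10 milliliters of sterile water".

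The Data Collection section lists items a to i: demographics, vital signs, diagnosis and history, the surgical approach, and (item i) the description and images of the angiography. CT, MR and endoscopic imaging follow outside the lettered list. Adverse events have their own recording rule under Management of Adverse Experiences.

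**The concern.** The protocol singles out one burden, extra minutes under anesthesia, and puts a number on it. A reader then looks for the variable that would test that number and finds none by name. Every patient is planned to receive ICG and there are no controls, so total operative time from the anesthesia chart could not isolate the increment. The adverse event definition covers signs, symptoms and medical conditions, so it would not pick up minutes either. Similarly, a maximum in mg/kg is set, but neither the amount given nor body weight is named.

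If this were a true defect, the study could finish without evidence on its own stated main risk. Later descriptions of that risk would still rest on the prior estimate, for example at IRB review: "The study will also be submitted for continuing review by the IRB at periods determined by the IRB, at least annually". An analysis plan could not restore times that nobody noted in theatre.

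**Working it through.** There is no sample-size or power figure to reproduce. The 15 minutes is an assertion with a cited range behind it, and 35 is a ceiling given without alpha, power or effect size. The check is mainly a comparison of sections.

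**1. Is the estimate wrong?** The protocol's figure is 15 minutes and the cited range is 15-20. The estimate is the lower end of that range. The upper end is 20 − 15 = 5 minutes longer, or 5/15 = 33%. Over 35 patients the total is 35 × 15 / 60 = 8.75 hours, against 35 × 20 / 60 = 11.7 hours. Choosing the lower end is mildly optimistic, but the source is quoted openly beside it and the estimate is not contradicted.

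**2. Do the two sections contradict each other?** The Risk and Benefit Assessment states an expected risk. Data Collection states what will be gathered. The second would contradict the first only if the protocol had undertaken to measure operative time, and it does so nowhere.

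**3. Does any conclusion depend on the minutes?** The Objective concerns performing the angiography and evaluating landmarks and tumor characteristics. The closing text of Data Collection does predict that the technique will prove highly feasible, but the reason it gives is that centres doing these operations already own the materials. That argument is about equipment and does not use time.

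**4. Is the list exhaustive?** Imaging is added after item i. Adverse events are recorded under another section although they are not among items a to i. The list is therefore not the full set of study data. Item i is free-form and can hold run times, number of injections and dose. Weight might be kept with vital signs or the anesthesia record. The case report form, where field-level detail usually sits, is not at hand.

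**5. Is the dose ceiling at risk?** The protocol gives no weights, so 50-100 kg is assumed.
- Ceiling: 2 mg/kg × 50 kg = 100 mg; 2 mg/kg × 100 kg = 200 mg.
- In typical boluses: 100/25 = 4; 200/25 = 8.
- One 25 mg bolus at each of the two named stages (an assumption, since the number is not fixed): 2 × 25 = 50 mg, and 50/50 = 1 mg/kg at the lightest assumed weight, half the ceiling.

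These figures show no likely breach. Dose also has no bearing on the risk in question, which is time.

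**6. What would recording time yield?** With 35 recorded values, the interval from the 12th to the 24th ordered value covers the median with probability 1 − 2 × P(Bin(35, 0.5) ≤ 11) = 95.9%. If no patient exceeded 20 minutes, the one-sided 95% upper bound on the share exceeding it would be 1 − 0.05^(1/35) = 8.2%. These figures show that the measurement would be informative. They describe a measurement the protocol does not claim to make, and they do not measure any harm from leaving it out.

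**The case for a change.** The strongest case for the concern is that feasibility ordinarily includes burden, and this protocol names its burden. The 15 minutes is borrowed from pituitary surgery, while this study covers a wider set of endonasal operations with ICG at more than one stage. It is well placed to check the figure at the cost of a few timestamps. Data not captured in theatre are hard to recover, so the matter could not simply be left to an analysis plan. Dose exposure can also vary, because the number of injections is not fixed and re-dosing at a second procedure is allowed.

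Much of this stands as fact. Nothing in the protocol requires these fields, capture under item i could differ from case to case, and adherence to the ceiling could not be demonstrated from the named items alone. It does not follow that the protocol is in error. That would require a stated aim, rule or conclusion that fails without the data, and there is none. The downstream consequences are also uncertain. The consent pages are not available, initial consent has to rely on a prior estimate in any case, and the protocol does not say what continuing review will contain. The natural substitute, clock time of each ICG run, would only approximate added operative time, because other surgical work may proceed meanwhile.

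**Conclusion.** The concern does not hold. Data Collection names no ICG time, injection count or dose, but the protocol does not promise to measure them and rests none of its conclusions on them. The 15-minute estimate sits at the lower end of its cited 15-20 minute range, at most 5 minutes below the upper end, and is not shown to be wrong. Feasibility is defined by performing the angiography and evaluating what it shows. On the assumed weight of 50 kg and one typical bolus per named stage, exposure would be half the stated maximum.

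This conclusion rests on reading the data list as open. That reading is supported by imaging and adverse events being collected outside items a to i, and by the free form of item i. What remains is a reasonable preference for extra fields on a data form, and the protocol can stand as written on this point.

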## **Human Subjects**

### 1. Institutional Review Board (IRB) Review and Informed Consent

This protocol and the informed consent document and any subsequent modifications will be reviewed and approved by the IRB or ethics committee responsible for oversight of the study. A signed consent form will be obtained from the subject. The consent form will describe the purpose of the study, the procedures to be followed, and the risks and benefits of participation, and the rights of the participant. A copy of the consent form will be given to the subject and this fact will be documented in the subject's record.

The Principal Investigator or the Study Coordinator will be responsible for submitting any changes to the project to the IRB for approval prior to implementation of the changes. The study will also be submitted for continuing review by the IRB at periods determined by the IRB, at least annually, for the duration of the study.

### 2. Subject Confidentiality

Subject data records will be identified by a study specific identification number. All subject records will be kept in a locked file cabinet. All computer entry and networking programs will be done using study specific identification number only. Clinical information will not be released without written permission of the subject, except as necessary for monitoring by IRB, the FDA, the OHRP, the sponsor, or the sponsor's designee.

### 3. Subjects' Rights

Subjects will have the right to withdraw from the study at any time without penalty or loss of any of their usual benefits.

## **Data Collection**

Specifically, patient demographic/clinical information to be included in this feasibility study will include:

- a. Age
- b. Gender
- c. Race
- d. Vital Signs
- e. Diagnosis
- f. Duration of Disease
- g. Brief Medical History
- h. Description of Surgical Approach
- i. Description and Images of Intraoperative Angiography

Medical imaging data to be presented will include pre- and post-operative CT and MR studies in addition to intraoperative angiography and intraoperative endoscopic images of the surgical site.

If, during the course of the procedure, the operator determines that it would be in patient's best interest to prematurely abort the procedure due to unforeseen events, it will be under the discretion of the PI to use the data from the prematurely aborted procedure. If patient has a second procedure after the first procedure was prematurely aborted, it is up to the PI discretion to re-dose patient with the ICG dye and complete the study procedures and collect study data from the second procedure. The PI may decide whether to use the data from the first procedure in this circumstance. ICG dye half-life is 3-4 minutes and does not pose a threat of overdosing.

In summary, this novel technique for performing real-time endoscopic intranasal angiography could substantially improve the safety of surgery by precisely locating the optic canal and internal carotid arteries; by providing additional information on tumor characteristics such as vascularization and vessel encasement.

This information may prompt further surgical action to avoid the complications associated with optic canal decompression, dissection near the internal carotid and tumor dissection. Presentation of this feasibility study in the literature will likely lead to wide acceptance and implementation of this technique due to the highly useful information it will yield as well as its high degree of feasibility, as institutions performing EEA procedures already possess the materials necessary to perform it.

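### Whether data from an aborted procedure are used is left to the PI with no criterion, so an unsuccessful attempt could drop out of the published feasibility series

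*Protocol*

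**What the plan says.** The Objective section states the aim: "We intend to demonstrate the feasibility of using a nasal endoscope to perform intraoperative angiography of surgical field". It adds the goals of evaluating anatomical landmarks and tumour characteristics, and names a technical note as the output.

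The Proposal section sets a ceiling on enrolment: "We anticipate needing no more than thirty-five patients to obtain the necessary information". It plans ICG at two points in the operation: "before intradural dissection and during tumor dissection".

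The Data Collection section then sets a rule for operations that are not completed. It applies when "the operator determines that it would be in patient's best interest to prematurely abort the procedure due to unforeseen events". In that case "it will be under the discretion of the PI to use the data from the prematurely aborted procedure". If a second operation follows, the PI may re-dose and collect data from it, and "The PI may decide whether to use the data from the first procedure in this circumstance". The section attaches no criterion to either choice, sets no time by which it must be made, and does not ask for it to be documented.

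**The concern.** A descriptive feasibility series is only as informative as the account of which attempts entered it. Here the person running the study decides case by case whether an incomplete attempt counts, and can do so knowing what the angiogram showed. When a second procedure follows, both sets of images may be in hand before the PI decides whether the first is used.

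An attempt in which ICG was given and the target structure was not seen could therefore be omitted, or replaced by a better second attempt. Readers would not know how many attempts lay behind the published cases. The Protocol expects them to act on the report: "Presentation of this feasibility study in the literature will likely lead to wide acceptance and implementation of this technique". The reasons it gives for that are the usefulness of the information and the availability of the equipment, not a success rate. Even so, the make-up of the series is what readers would have to judge by.

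This is not a detail that a protocol normally leaves to an analysis plan. The Protocol states a data-inclusion rule itself, and that rule is open discretion.

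**Working it through.** **Does the text allow selection after the result is known?**

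1. Proposal: ICG is given at two stages, and the angiogram is viewed in real time.
2. Data Collection: an operation may be aborted at any point, on the operator's judgement of the patient's interest.
3. An abort between the stages, or after the second, can therefore leave an angiogram that the team has already seen.
4. Data Collection: the PI then decides on use, with no criterion.
5. Other sections: adverse event recording, IRB review of changes, confidentiality and the right to withdraw do not limit this choice. None of them requires every attempt to be accounted for.

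The selection is therefore permitted. Whether it would occur cannot be told from the document.

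**How large could it be?** The Protocol has no figure to reproduce. It gives no abort rate, success proportion or threshold, and the ceiling of 35 has no statistical derivation. The following is an illustration that assumes a proportion visualised is reported at all.

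Let n be the patients assessed and s those visualised. Take n = 35 (the ceiling) and consider one aborted patient. The values of s are assumptions.

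- Not visualised and left out: s/(n−1) − s/n
- Not visualised and superseded by a successful second procedure: (s+1)/n − s/n = 1/n
- Visualised and left out: (s−1)/(n−1) − s/n

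| True result | Failure left out | Failure superseded | Success left out |
|---|---|---|---|
| 34/35 | 34/34 − 34/35 = +2.9 points | 1/35 = +2.9 | 33/34 − 34/35 = −0.1 |
| 28/35 | 28/34 − 28/35 = +2.4 | 1/35 = +2.9 | 27/34 − 28/35 = −0.6 |
| 18/35 | 18/34 − 18/35 = +1.5 | 1/35 = +2.9 | 17/34 − 18/35 = −1.4 |

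With fewer patients each one weighs more: at an assumed n = 20, a superseded failure shifts the figure by 1/20 = 5.0 points.

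A patient whose procedure is aborted before ICG, and who is never given it later, has not been assessed. That patient enters neither numerator nor denominator, and the shift is 0.

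**The case against.** The strongest reply is that no rate is planned. The output is a technical note with descriptions and images, so leaving out one case distorts no defined estimate. This stands as far as size goes: every percentage above depends on a summary that the Protocol does not promise. It does not remove the point, because a descriptive series also misleads if unsuccessful attempts are missing.

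The route is also narrow. It needs an abort, ICG already given, the target assessed and not seen, and a decision not to use the case. The trigger is the patient's interest, not image quality. And a choice not to use data is not a statement that the case will go unmentioned. All of this is fair, and it is why the effect is only possible.

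Some readers may infer more than the text supports:

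- **A large overstatement.** If 7 of 35 procedures were aborted and each counted as a failure, the result would be 28/35 = 80% with all attempts counted, and 28/28 = 100% with aborts dropped, a gap of 20 points. The Protocol supports neither the number of aborts nor the treatment of every abort as a failure; an abort before ICG says nothing about visualisation.
- **Licence to discard any poor angiogram.** The clause covers aborted procedures only, not completed operations with poor images.
- **Loss of safety data.** The adverse event section does not exempt aborted procedures from recording.
- **A biased decision at the thirty-fifth patient.** The Protocol would seek further approval or "terminate this feasibility study if the necessary information cannot be obtained by the thirty-fifth patient". It does not define that information, so no effect on this decision can be shown.

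**Conclusion.** The point holds in a limited form. The Protocol gives the PI discretion, without a criterion, over the use of data from aborted procedures and over first-procedure data when a second follows, and no other section restrains it. Since the angiogram may already have been seen, the published series of at most 35 patients could look more favourable than the experience was.

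The size cannot be derived from the document. If a proportion were reported, one assessed but unsuccessful patient left out or superseded would raise it by about 1.5 to 2.9 points with 35 assessed, while leaving out a successful aborted case would lower it by 0.1 to 1.4 points. These figures rest on an assumed endpoint and assumed success levels. The effect is zero if no procedure is aborted after ICG, or if every aborted case is reported. The reason to act is that the rule is open and closing it costs almost nothing, not that a bias has been shown.

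**What to change.** In Data Collection, replace the PI's discretion over data use with a rule fixed in advance:

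1. Every patient taken to surgery is accounted for in the report.
2. Every aborted procedure is reported with its reason and any angiogram obtained, separately for each of the two ICG stages.
3. A stage that was not assessed, because ICG was not given or the stage was not reached, is kept separate from a stage that was assessed but where the target was not visualised.
4. Any repeat ICG procedure is reported in addition to the first, not in place of it, and is labelled as a repeat.

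Reporting by stage means that an abort between the stages does not hide what a later procedure showed, so there is no need to name one procedure as primary or to add a sensitivity analysis. The change concerns data use only; the decisions to abort and to re-dose stay as they are.

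The cost is a few sentences, with no extra patients or procedures. The downside is that reported feasibility may look slightly less favourable.

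### Do the two stated ICG half-lives undermine the protocol's statement that re-dosing is not an overdose risk?

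*Protocol*

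**What the plan says.** The protocol's Background and Rationale section, citing a published series, states that "ICG is metabolized exclusively by the liver with a plasma half-life of 150 seconds". The Data Collection section deals with an operation that is stopped early and followed by a second one. In that case "it is up to the PI discretion to re-dose patient with the ICG dye and complete the study procedures", and the paragraph closes with the uncited sentence "ICG dye half-life is 3-4 minutes and does not pose a threat of overdosing".

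The Risk and Benefit Assessment quotes the product label: "There are no data available describing the signs, symptoms, or laboratory findings accompanying overdose". The label's animal lethal-dose ranges follow, beginning "The LD 50 after I.V. administration ranges between 60 and 80 mg/kg in mice". The section then says "The FDA arbitrarily suggests a maximum dose of 2mg/kg for human use, and this would be our dosage maximum". It does not say whether that limit counts each injection, each operation, or everything a patient receives.

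The Proposal section plans imaging "at different stages of endonasal cranial base surgery and tumor dissection: before intradural dissection and during tumor dissection", so more than one injection in a single operation is foreseeable.

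**The concern.** Three things look wrong together. First, the same dye has two half-lives that do not overlap, one cited and one not. Second, the uncited figure carries weight: it is the only reason the re-dosing paragraph gives for a categorical safety statement. Third, that statement sits uneasily beside a section that reports no description of overdose and adopts a dosage limit, which the re-dosing paragraph never mentions.

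If the half-life governed whether dye accumulates between doses, a wrong figure could make repeat dosing look safer than it is. Within one operation, it could also affect how much dye from the first angiogram is still present at the second. If the limit were cumulative and nobody noticed, patients dosed at two operations might exceed it.

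**Working it through.** **Inputs from the protocol.** Half-life 150 s (Background and Rationale) and 3-4 min (Data Collection); typical bolus 25 mg (Background and Rationale); maximum 2 mg/kg (Risk and Benefit Assessment); two imaging stages per operation (Proposal).

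**Assumptions.** First-order decay; one 25 mg bolus per stage; body weight 50-100 kg; a second operation at least one hour after the first dose. The protocol states none of these.

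**Step 1: do the half-lives agree?** 150 / 60 = 2.5 min, which is outside 3-4 min. The ratios are 3 / 2.5 = 1.2 and 4 / 2.5 = 1.6. Rounding does not explain the gap.

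**Step 2: does the gap matter for re-dosing at a second operation?** Fraction remaining = 0.5^(t / half-life).

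| Time since dose | 2.5 min | 3 min | 4 min |
|---|---|---|---|
| 5 min | 25% | 31% | 42% |
| 10 min | 6.3% | 9.9% | 17.7% |
| 30 min | 0.02% | 0.10% | 0.55% |
| 60 min | 0.00000006 | 0.000001 | 0.00003 |

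(The last row gives fractions.) At 60 minutes the three values correspond to 60 / 2.5 = 24, 60 / 3 = 20 and 60 / 4 = 15 half-lives. In the slowest case, 25 mg × 0.00003 is less than 0.001 mg. The half-lives differ visibly only over minutes, and the re-dosing paragraph concerns a separate operation.

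**Step 3: how far does the undefined scope of the maximum reach?**

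- The limit is 2 × 50 = 100 mg at 50 kg and 2 × 100 = 200 mg at 100 kg.
- One operation: 2 × 25 = 50 mg, which is 50 / 100 = 0.5 mg/kg to 50 / 50 = 1.0 mg/kg.
- Two operations, counted cumulatively with no clearance: 4 × 25 = 100 mg, which is 1.0 to 2.0 mg/kg.

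Even the strictest reading meets the limit at 50 kg without passing it. It is passed at lower weights (at 45 kg, 100 / 45 = 2.2 mg/kg) or with more or larger boluses.

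**Step 4: do the safety statements contradict each other?** The label quotation says that the signs, symptoms and laboratory findings of overdose have not been described. It does not say that nothing is known, since animal lethal-dose ranges follow it. The re-dosing sentence says overdose is not expected, because the dye clears quickly. One concerns what an overdose would look like, the other whether one would occur, so both can stand. The 2 mg/kg limit is stated without exempting re-dosing, so it still applies where that paragraph is silent.

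**The case for a change.** The strongest case for acting does not rest on the half-life. A protocol that adopts a maximum dose should not dismiss overdose elsewhere without referring to it, least of all where repeat dosing is left to discretion. Neither the dose nor the injection time is named in the list of data items, so adherence to the limit could not be checked from that list alone. Correcting this would cost a few words and two fields.

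Part of this stands. The mismatch exists, and the scope of the limit is unstated. But the scope is a detail the investigators can settle under the limit they have already adopted, and the description of each angiogram, which is a listed data item, can hold dose and time. Putting a particular governing rule in place of the re-dosing statement would be a clinical choice, which a statistical review should not make.

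The argument about second-stage images is weaker. The protocol gives neither the interval between the two stages nor a level of residual dye that would spoil an image. The 15 minutes in the Risk and Benefit Assessment are added operating time, not the gap between injections. The differences at 5 and 10 minutes in the table therefore cannot be turned into a loss of image quality from this document.

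**Conclusion.** No change to the plan follows. The half-lives conflict by a factor of 1.2 to 1.6, but this is a clerical slip. At a second operation an hour or more later, the remaining fraction is at most about 0.00003 under any stated value, so the statement on accumulation comes out the same. The scope of the 2 mg/kg maximum is a gap in wording. With 25 mg boluses, two per operation and two operations, it bites only below 50 kg, and then only if the limit is read as cumulative.

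These conclusions rest on first-order decay, the typical bolus being the study dose, and the one-hour interval. Larger or more frequent boluses would widen the gap in Step 3 but would not make the choice of half-life matter at a separate operation. The study is a feasibility series of at most thirty-five patients, and none of its stated figures is computed from a half-life.

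The Background and Rationale, Risk and Benefit Assessment and Data Collection sections do have to be reconciled by the sponsor as a matter of housekeeping. No view is taken here on which half-life or dosing rule is correct.
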